2.2 TREATMENT PROCEDURES

The subject is given 4 CapScan Devices and one 1,000 mg dose of sulfasalazine. The subject is provided with snack bars to consume before swallowing the CapScan Devices. The subject is given a retrieval wand to snare the expelled CapScan Devices from the toilet bowl and stool collection containers if they prefer to retrieve the device from stool in the container as opposed to from the toilet. The subject is also given 2 Tasso+ home-use blood collection devices, saliva

and stool collection tubes for analysis of blood, saliva and stool microbiome and metabolites. The blood, saliva and stool samples will be compared to the intestinal samples collected by the CapScan Device. The subject is given Daily Diaries to document the time the CapScan Devices were swallowed, blood and saliva samples collected, what the subject ate, and time of bowel movements.

On Day 1, after consuming a snack bar, the subject swallows 2 CapScan Devices and collects stool and saliva for the baseline set of measurements.

On Day 2, after consuming a snack bar, the subject takes a single dose of 1,000 mg of sulfasalazine and swallows 2 CapScan Devices and collects blood, stool and saliva.

The timing of the dose of sulfasalazine, sampling of blood, stool and saliva and the ingestion of the CapScan Devices on each day will be at the discretion of the PI.

The subject continues to collect all CapScan Devices expelled in the stool until all ingested CapScan Devices have been retrieved, or until Day 8. In the event of missing CapScan Devices that weren't successfully retrieved by the end of Day 8, and at the discretion of the PI, an abdominal x-ray will be performed on the subject to confirm no CapScan Devices are still in the body.

In the event that a subject was unable to retrieve the two CapScan Devices swallowed on Day 2 or if the devices did not produce usable samples, the PI may request that the full set of procedures from Day 2 will be repeated on one day between Day 12-19 to give sufficient time for any sulfasalazine to be cleared from the body, including a second dose of 1,000 mg of sulfasalazine and swallowing and retrieval of 2 additional CapScan Devices. The End of Study is defined when the last ingested CapScan Device is collected from the stool, or after determination by the PI that no CapScan Devices are in the subject's body.

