2.4 RISK BENEFIT ANALYSIS

2.4.1 Possible Risks

The potential risks associated with the use of CapScan Device include transient discomfort when swallowing a CapScan Device. Additional risks include aspiration and intestinal blockage.

The risks above are considered reasonable given the following safeguards:

Physically, the size and shape of the CapScan Device is similar to a standard size 00 medicinal capsule. As such, the swallowing of the CapScan Device does not pose any greater risk to the health, safety, or welfare of the patient than the swallowing of a standard medicinal capsule.

The passage of the CapScan Device through the GI tract does not present any greater risk to the health, safety, or welfare of the patient than a Medtronic Pillcam[®], which is routinely swallowed for diagnostic purposes and eliminated via defecation. The Pillcam[®] is hard and inflexible and is 12 mm in diameter, *versus* the CapScan Device which is soft and flexible and only 6 mm in diameter. A radio-opaque marker incorporated into the CapScan Device enables definitive confirmation that the device has been eliminated from the body, if necessary.

Generally, healthy volunteers with any underlying intestinal stricture that would prevent the passage of items 6 mm in diameter through the GI tract would be symptomatic even before the study. Examples of symptoms of pre-existing intestinal blockage could include pain and bloating after eating corn or other vegetables, for example.

In the unexpected event that the CapScan Device is retained in the intestines, the CapScan Device can be removed via motility enhancers (i.e. laxatives) or via laparoscopic surgery in a worst case scenario. In the event of a retained CapScan Device, there is a potential benefit for the subject to discover and treat the underlying cause of any pre-existing intestinal strictures inadvertently discovered as part of this study.

All of the materials in the CapScan Device have been well characterized and understood to be biocompatible and used in a variety of cleared medical products and pharmaceuticals.

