The subject will continue to retrieve the CapScan Devices, collect stool and complete the daily diaries until the last device is retrieved. If not all devices have been retrieved by Day 8, the PI may elect to perform an abdominal x-ray to confirm that no CapScan Devices are still in the body. The End of Study is defined when the last ingested CapScan Device is collected from the stool, or after determination by the PI that no CapScan Devices are in the subject's body.

DAYS 12-19, if needed:

In the event that a subject was unable to retrieve the two CapScan Devices swallowed on Day 2 or if the devices did not produce usable samples, the PI may request that the full set of procedures from Day 2-8 will be repeated starting on any day between Day 12-19 to give sufficient time for any sulfasalazine to be cleared from the body, including a second dose of 1,000 mg of sulfasalazine and swallowing and retrieval of 2 additional CapScan Devices. The end of the study is defined when the last swallowed CapScan Device is retrieved from the stool or after determination by the PI that no CapScan Devices are in the subject's body. At this point, a study representative will go to the subject's house to collect all unused CapScan Devices,

retrieved devices, blood, saliva and stool samples, refrigerator and the Daily Diaries from the subject.

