6.1 INCLUSION CRITERIA

Subjects must meet all of the following criteria to be included in the study:

- Males or females 18 years of age or older and 70 years of age or younger at the time of the first Screening Visit.
- ASA Classification 1 or 2.
- For women of childbearing potential, negative urine pregnancy test within 7 days of Screening Visit and agreement to remain abstinent (refrain from heterosexual intercourse) or use adequate contraception during the treatment period and for 14 days after the final dose of sulfasalazine.
- Subject is fluent in English and understands the study protocol and informed consent and is willing and able to comply with study requirements and sign the informed consent form.

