6.4 REMOVAL, REPLACEMENT, OR EARLY WITHDRAWAL OF SUBJECTS FROM THERAPY OR ASSESSMENT

Subjects are free to discontinue their participation in the study at any time and without prejudice to further treatment, up until the time of publication of the study results, at which point withdrawal from the study is no longer possible. The Principal Investigator (PI) must withdraw any subject from the study, if that subject requests to be withdrawn. If a subject is withdrawn from the study or fails to return either at his or her request or at the PI's sole discretion, every effort should be made to determine the reason. This information will be recorded in the subject's CRF.

When a subject is removed from the study for a Serious Adverse Event, a final medical evaluation must be performed. Patients removed from the study because of an adverse event will be followed-up until the adverse event has resolved or stabilized.

If a subject has discontinued study participation during the CapScan Device Use Phase, the subject will return all collected and unused CapScan Devices, collected saliva, blood and stool samples, the completed Daily Diaries and the refrigerator.

Subjects withdrawn from the study will be replaced, regardless of the reason for withdrawal.

The subject's participation in this study may be discontinued due to any of the following reasons:

- Failure to follow the instructions of the PI and study staff
- The PI decides that continuing participation could be harmful to the subject
- Pregnancy
- The study is cancelled

- Other administrative reasons
- Unanticipated circumstances

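### The Day 12-19 repeat can follow unretrieved devices, but the plan requires no proof that earlier devices have passed and no new pregnancy, medication or eligibility check before re-exposure

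*Combined protocol and SAP*

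**What the plan says.** The repeat rule appears in the synopsis (Study Treatment), in Section 2.2 and in Section 5 under Days 12-19. It has two triggers: the subject could not retrieve the two Day 2 devices, or the devices gave no usable samples. In either case "the PI may request that the full set of procedures from Day 2-8 will be repeated starting on any day between Day 12-19", with a second 1,000 mg dose and two additional devices. The only reason given for the interval is clearance of sulfasalazine; passage of the devices is not mentioned.

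For devices still missing at Day 8, Section 5 says "the PI may elect to perform an abdominal x-ray to confirm that no CapScan Devices are still in the body". The synopsis and Section 2.2 also leave the x-ray to the PI's discretion. A determination by the PI appears in one role only, as an alternative way to reach End of Study: retrieval of the last device, "or after determination by the PI that no CapScan Devices are in the subject's body". Section 7.3 (Use Phase) defines the end of the study by retrieval alone.

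The entry criterion in Section 6.1 is a "negative urine pregnancy test within 7 days of Screening Visit". Table 1 marks the urine test, concomitant medications and inclusion/exclusion in the Screening column only. AE/SAE recording is the only item it carries into the later columns. Neither Table 1 nor Table 2 has a column for the repeat.

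**The concern.** Section 2.4.1 lists the device risks and states: "Additional risks include aspiration and intestinal blockage". It gives laparoscopic surgery as the worst-case remedy for a retained device. A subject whose devices have not appeared is the one in whom retention is most plausible, and non-retrieval is one of the two grounds for giving that subject two more. Section 6.2 excludes known or suspected obstruction, stricture and moderate to severe dysmotility. A missing device is new information on those criteria, and it arises after the only scheduled eligibility check.

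The second dose raises a similar issue. A woman of childbearing potential can receive it with no test since Screening. Medication use may also have changed: Section 2.4.1 names laxatives as a way to clear a retained device, while Section 6.2 names them among drugs that may interfere with the study.

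What is at stake is the safety of the few subjects who are repeated. No endpoint, estimate or error rate depends on it.

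**Working it through.** The plan gives no figure of its own to reproduce here. The check compares provisions and counts days.

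**Is clearance required before a repeat?**
- Repeat rule, in all three places: two triggers and the PI's request, with no further condition.
- X-ray: optional in all three places.
- PI determination that no device remains: part of the End of Study definition. Section 5 gives that definition under Days 3-8 and again under Days 12-19. A PI could therefore make the determination before a repeat, but neither place makes the repeat depend on it. Read literally, making it would end the study for that subject.
- Result: clearance is possible before a repeat but not required. The gap concerns the non-retrieval trigger. Where the devices came back and only the samples failed, those devices raise no retention question.

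**How many devices may be unconfirmed?**
- Literal trigger, Day 2 devices missing: 2. After the repeat: 2 + 2 = 4.
- Day 1 devices missing as well: 2 + 2 = 4. After the repeat: 4 + 2 = 6.

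**How long is the interval?**
- Day 2 to the repeat: 12 − 2 = 10 days, to 19 − 2 = 17 days.
- Day 8, the last planned retrieval day, to the repeat: 12 − 8 = 4 days, to 19 − 8 = 11 days. There is time to establish clearance.

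**How old is the pregnancy test at the second dose?**
- Assumption: Screening falls on Day 1, as the Table 2 header suggests. Section 5 lists Screening separately from Day 1, and the plan sets no maximum gap between them.
- First dose on Day 2: 2 − 1 = 1 day old.
- Second dose: 12 − 1 = 11 days, to 19 − 1 = 18 days old. Any gap between Screening and Day 1 adds to both.

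**Does a repeat need new supplies?**
- Section 2.2: "The subject is given 4 CapScan Devices and one 1,000 mg dose of sulfasalazine".
- Devices left after Day 2: 4 − 2 − 2 = 0. Doses left: 1 − 1 = 0. A repeat needs 2 devices and 1 dose, so something must be dispensed. Sections 7.2 and 7.5 let the sponsor dispense directly to the subject, so this step need not involve the PI.

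**Frequency.** The documents give no retrieval or retention rate, so none is computed.

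**The case against.** The strongest reply is that a physician already controls each step. The repeat is never automatic, the x-ray is available from Day 8, and Section 6.4 lets participation be stopped when "The PI decides that continuing participation could be harmful to the subject". The subjects are up to 10 ASA 1-2 volunteers, the device is soft and 6 mm wide, and known or suspected obstruction is excluded. Many missing devices will simply have been overlooked in the stool. Subjects must report pregnancies (Section 10.7) and adverse events and drugs taken (Section 12.4), adverse events are recorded from consent (Section 8.1.1), and planned pregnancy within 30 days of Screening is an exclusion.

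These points make harm unlikely, and they stand to that extent. They are general discretion or self-report, though, and none is a required check before re-exposure.

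The device count alone shows little. The base schedule already has subjects swallow two devices on Day 2 without requiring that the Day 1 pair has passed, so it accepts four at once. What differs at the repeat is the prolonged absence of the Day 2 devices, 10 to 17 days after swallowing.

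Two stronger readings are tempting and should not be drawn:
- A reader might take the seven-day allowance in Section 6.1 to mean that the test could be a week older at each dose. Section 7.1 bars protocol procedures before consent, consent is signed at Screening, and Table 1 puts the test there. Only a test done outside the study could be older.
- A reader might count 14 days from the Day 2 dose and conclude that contraception lapses before the later repeat days. The commitment is to "use adequate contraception during the treatment period and for 14 days after the final dose of sulfasalazine". For a repeated subject the final dose is the second one, so the ordinary reading is continuous cover. That the treatment period is undefined is a wording weakness and does not show a gap.

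**Conclusion.** The point holds as a patient-safety gap in a stated rule. As written, the plan allows a subject with at least 2 unconfirmed devices, and up to 4 if the Day 1 pair is also missing, to swallow two more without anyone having established that the earlier ones passed. It also allows a second 1,000 mg dose with no new pregnancy test, medication review or eligibility check. The only scheduled pregnancy test is then 11 to 18 days old, assuming Screening on Day 1.

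A reader might infer that retention is likely, or that the PI is kept from checking. The documents support neither: they give no retention rate, and the PI is free to order the x-ray. The defect is that the check is optional where non-retrieval is itself the reason for re-exposure. Few subjects would be affected, and no endpoint or estimate changes. The change should be made because it is cheap and specific.

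**What to change.** Add to the repeat rule in the synopsis, Section 2.2 and Section 5 that before any repeat the PI must:

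- (a) document that every device swallowed so far has been retrieved or is no longer in the body, using the abdominal x-ray already provided for when this cannot be established otherwise; if it is not established, there is no repeat;
- (b) obtain a negative urine pregnancy test in women of childbearing potential, before any x-ray and before the second dose;
- (c) briefly review adverse events, concomitant medications and the exclusion criteria.

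Add a matching repeat column to Tables 1 and 2.

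The cost is one PI contact per repeated subject, and one urine test where the subject is a woman of childbearing potential. Because the sponsor may dispense directly, the contact cannot be assumed to coincide with resupply and should be scheduled in its own right. Where devices stay unaccounted for, the choice is between an x-ray in a healthy volunteer and no repeat. Declining the repeat can lose that subject's Day 2 luminal data from a study of up to 10, and Section 6.4 provides replacement only for withdrawn subjects.

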6. STUDY POPULATION

Study subjects will be healthy volunteers (ASA classes 1 and 2).

6.1 INCLUSION CRITERIA

Subjects must meet all of the following criteria to be included in the study:

- Males or females 18 years of age or older and 70 years of age or younger at the time of the first Screening Visit.
- ASA Classification 1 or 2.
- For women of childbearing potential, negative urine pregnancy test within 7 days of Screening Visit and agreement to remain abstinent (refrain from heterosexual intercourse) or use adequate contraception during the treatment period and for 14 days after the final dose of sulfasalazine.
- Subject is fluent in English and understands the study protocol and informed consent and is willing and able to comply with study requirements and sign the informed consent form.

6.2 EXCLUSION CRITERIA

Subjects with any of the following conditions or characteristics must be excluded from the study:

- Known or suspected gastrointestinal obstructions, strictures or fistula
- Known or suspected moderate to severe dysmotility, by the judgement of the principal investigator
- Gastroparesis
- A swallowing disorder
- Known intolerance, reaction or hypersensitivity to sulfasalazine, its metabolites, sulfonamides, or salicylates
- Urinary obstruction
- Porphyria
- G6PD deficiency
- Known or suspected infection with SARS-CoV2, HIV, HBV or HCV
- Pregnancy or planned pregnancy within 30 days from Screening Visit, or breast-feeding.

- Use of concomitant medications, such as aspirin, antibiotics, laxatives and proton pump inhibitors that may interfere with the study in the judgement of the investigator.
- Any form of active substance abuse or dependence (including drug or alcohol abuse), unstable medical or psychiatric disorder, or any chronic condition susceptible, in the opinion of the principal investigator, to interfere with the conduct of the study.
- A clinical condition that, in the judgment of the principal investigator, could potentially pose a health risk to the subject while involved in the study.

6.3 SUBJECT IDENTIFICATION

A unique subject identifying number will be assigned when an individual subject is qualified for enrollment. Before formal enrollment into the study, subjects will be uniquely identified by their initials and a subject identification number only.

6.4 REMOVAL, REPLACEMENT, OR EARLY WITHDRAWAL OF SUBJECTS FROM THERAPY OR ASSESSMENT

Subjects are free to discontinue their participation in the study at any time and without prejudice to further treatment, up until the time of publication of the study results, at which point withdrawal from the study is no longer possible. The Principal Investigator (PI) must withdraw any subject from the study, if that subject requests to be withdrawn. If a subject is withdrawn from the study or fails to return either at his or her request or at the PI's sole discretion, every effort should be made to determine the reason. This information will be recorded in the subject's CRF.

When a subject is removed from the study for a Serious Adverse Event, a final medical evaluation must be performed. Patients removed from the study because of an adverse event will be followed-up until the adverse event has resolved or stabilized.

If a subject has discontinued study participation during the CapScan Device Use Phase, the subject will return all collected and unused CapScan Devices, collected saliva, blood and stool samples, the completed Daily Diaries and the refrigerator.

Subjects withdrawn from the study will be replaced, regardless of the reason for withdrawal.

The subject's participation in this study may be discontinued due to any of the following reasons:

- Failure to follow the instructions of the PI and study staff
- The PI decides that continuing participation could be harmful to the subject
- Pregnancy
- The study is cancelled

- Other administrative reasons
- Unanticipated circumstances

6.5 HANDLING OF WITHDRAWALS

If a subject is withdrawn from the study or fails to return either at his or her request or at the PI's sole discretion, every effort should be made to determine the reason. This information will be recorded on the subject's case report form (CRF).

All subjects who withdraw from the study prematurely, regardless of cause, should undergo all early termination assessments; if relevant. It is vital to obtain follow-up data for any subject withdrawn due to an AE following device use.

6.6 SPONSOR'S TERMINATION OF STUDY

Envivo Bio Inc. reserves the unilateral right to discontinue the study at any time for any reason. Envivo Bio Inc. may also discontinue the study for inadequate site performance or compliance. Such a termination must be implemented by the PI, if instructed to do so by Envivo Bio Inc., in a time frame that is compatible with the subjects' well-being.

7. STUDY PROCEDURES

7.1 STUDY PROCEDURES CHART

A schedule of study procedures for the investigator and study subject are shown in Table 1 and Table 2 respectively. No protocol related procedures will be performed before subjects review and sign a written informed consent form.

Table 1: SCHEDULE OF INVESTIGATOR STUDY PROCEDURES			
	SCREENING	CAPSCAN DEVICE USE	CAPSCAN DEVICE RETRIEVAL
PROCEDURES	1 Day	2 days	Up to 8 days
Informed Consent	Х		
Inclusion/Exclusion	Х		
Demographics	Х		
Medical History	Х		
Concomitant			
Medications	Х		
General Health			
Assessment (ASA			
classification)	Х		
Urine Pregnancy	Х		
AE/SAE		Х	Х

Table 2: SCHEDULE OF SUBJECT STUDY PROCEDURES				
	SCREENING	CAPSCAN DEVICE USE	CAPSCAN DEVICE RETRIEVAL	
PROCEDURES	Day 1	Day 2	Days 3-8	
Informed Consent	X			
Swallows 2 CapScan Devices				
	Х	Х		
Collect saliva samples when swallowing	х	×		
CapScan Devices	Λ	Χ		
Collect blood using Tasso+ home-use tests		x		
Retrieve CapScan Devices from stool				
using retrieval wand	Х	Х	Х	
Ingests 1000mg of sulfasalazine		х		
Complete Daily Diaries				
to document the time				
the CapScan devices				
were swallowed, what				
was eaten, and time				
of bowel movements	Х	Х	Х	

7.2 SCREENING VISIT

The purpose and procedures of the study will be fully explained to potential subjects. Those individuals wishing to enroll in the study will sign a written informed consent form prior to initiating any evaluations or procedures. The Screening Visit includes:

- Review and sign Informed Consent by subject and PI or PI designee
- Assess suitability of subject to enroll in the study according to the Inclusion and Exclusion Criteria
- Obtain subjects medical history (including clinically significant abnormalities of all body systems), demographic data and concomitant medications
- Conduct health assessment of subject to include ASA classification
- Provide instruction for and dispense Daily Diaries to complete at home.

- Provide instruction for use and dispense, or have the Sponsor dispense, 4 CapScan Devices.
- Provide instructions for use and dispense, or have the Sponsor dispense, blood collection devices, retrieval wands, stool and saliva collection containers for collecting CapScan Devices expelled in stool.
- Provide instruction for and dispense, or have the Sponsor dispense, saliva and blood collection kits.
- Provide instructions for use and dispense, or have the Sponsor dispense, 1,000 mg of sulfasalazine.
- Assign subject a unique study number.

